# 11.2. Adverse Event Reporting Requirements

#### 11.2.1. Serious Adverse Events

All events meeting the criteria for Serious Adverse Events (see Section 11.1.2) must be reported by investigational sites within 24-hours of becoming aware of the event. In order to determine the Sponsor's timeline for notifying regulatory authorities and investigators per Federal Regulations, an event term, serious criteria, and causality is required at the time of the initial report. Specific SAE reporting instructions are provided in a separate manual.

The Investigator is responsible for notifying the IRB/IEC/REB in writing of serious events as soon as is practical in accordance with the policy of the IRB/IEC/REB.

# 11.2.2. All Adverse Events (AEs) Regardless of Seriousness

Any adverse medical condition or laboratory abnormality with an onset date before the date of randomization is considered to be pre-existing in nature, and part of a subject's medical history. Adverse medical conditions that begin on or after date of randomization will be considered an adverse event, including SAEs, and followed for 30 days after the last dose of IMRT, cisplatin, or GC4419/Placebo (i.e., whichever occurs last), hereafter referred to as the "30 Day Follow-up Period". Similarly, new events will be reported as AEs/SAEs if the start date is within 30 Day Follow-up Period. Increases in toxicity grade of pre-existing conditions that occur on or after the date of randomization are also considered an adverse event.

All adverse events must be recorded in the subject's source documents and on the CRF regardless of frequency, severity (grade) or assessed relationship to randomized therapy.

# 11.2.3. Clinical Laboratory Abnormalities and Other Abnormal Assessments as AEs and SAEs

Clinically significant abnormal laboratory findings or other abnormal assessments that are associated with the disease being studied, unless judged by the Investigator as more severe than expected for the subject's condition, or that are present or detected at the time of randomization and do not worsen, will not be reported as AEs or SAEs.

Laboratory abnormalities should only be recorded in the Adverse Event section of the CRF if at least one of the following criteria is met:

Meets the criteria of an SAE

Resulted in a dose reduction and/or delay in the administration of GC4419/Placebo, IMRT, and/or cisplatin

Treatment is initiated for the abnormality

Investigational product was discontinued

Grade 3 or Grade 4 per NCI CTCAE v5.0

All other abnormal laboratory findings will be captured via laboratory CRF pages and noted in shift tables.

Galera Therapeutics, Inc.

Version: Amendment 4

Abnormal assessments (e.g., ECGs) that are judged by the Investigator as clinically significant will be recorded as AEs or SAEs if they meet the definitions as defined in Section 11.1.

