## 1. SYNOPSIS

Name of Sponsor/Company: Galera Therapeutics, Inc.

Name of Investigational Product: GC4419 (avasopasem manganese)

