## **Exploratory Objectives:**

- To assess duration (per subject) of SOM (WHO Grade 3-4) for subjects who have experienced SOM during the OM Observation Period
- To assess duration of Grade 4 OM for subjects who have experienced Grade 4 OM during the OM Observation Period
- To assess effects of GC4419 on the cumulative incidence of SOM (WHO Grade 3-4) from the first IMRT fraction through the delivery of progressive, cumulative IMRT doses
- To assess effects of GC4419 on the cumulative incidence of SOM (WHO Grade 3-4) during the OM Observation Period
- To assess time from beginning of IMRT and IMRT dose to onset of SOM (WHO Grade 3-4)

To assess resolution (defined as ≤ Grade 2 OM) of SOM (WHO Grade 3-4) before the end of the Study Treatment Period for subjects who have experienced SOM during the Study Treatment Period

Galera Therapeutics, Inc.

Version: Amendment 4

- To assess resolution (defined as ≤ Grade 3 OM) of Grade 4 OM before the end of the Study Treatment Period for subjects who have experienced Grade 4 OM during the Study Treatment Period
- To assess effects of GC4419 on the incidence, onset, and duration of ulcerative OM (≥ Grade 2)
- To assess treatment delivery and delays (number and duration of delays) of IMRT and cisplatin

To assess the relationship between drug exposure and safety/efficacy

To assess the effects of GC4419 on circulating cytokine levels and gene expression levels

To assess the effects of GC4419 on kidney function throughout the first year post-IMRT

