# 12.4. Safety Analysis

AEs will be grouped by system organ class, high level term, and preferred term according to the Medical Dictionary for Regulatory Activities (MedDRA) dictionary. Incidence by subject will be tabulated for all treatment-emergent, serious, severe, and treatment-related adverse events. Detailed listings will be provided for all serious adverse events, deaths, and withdrawals due to adverse events.

Laboratory measurements and vital signs will be summarized by treatment group at each of the protocol-specified time points.

Safety parameters will be summarized with descriptive statistics on all subjects who received at least one dose of GC4419/Placebo. Safety analyses will be conducted on the ITT population and the dosing suspension subjects separately.

Further details will be provided in the study's Statistical Analysis Plan.

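### No criterion in Section 11.2.3 covers discontinuation of cisplatin or IMRT, so a low-grade laboratory abnormality that leads directly to stopping either one can go unrecorded as an AE

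*Combined protocol and SAP*

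**What the plan says.** Section 11.2.3 sets a restrictive rule: "Laboratory abnormalities should only be recorded in the Adverse Event section of the CRF if at least one of the following criteria is met". Five criteria follow:

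1. "Meets the criteria of an SAE"
2. "Resulted in a dose reduction and/or delay in the administration of GC4419/Placebo, IMRT, and/or cisplatin"
3. "Treatment is initiated for the abnormality"
4. "Investigational product was discontinued"
5. Grade 3 or 4 under CTCAE version 5.0

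Any other abnormal value goes to the laboratory CRF pages and the shift tables. This narrows Section 11.2.2, which otherwise asks for every AE to be recorded whatever its grade. Section 12.4 tabulates AE incidence and adds: "Detailed listings will be provided for all serious adverse events, deaths, and withdrawals due to adverse events".

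**The concern.** Criteria 2 and 4 differ in scope. Criterion 2 names study drug, IMRT and cisplatin. Criterion 4 names study drug alone. Read as written, the rule can record the lesser consequence of a laboratory abnormality and leave out the greater one.

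What is at stake is the completeness of safety reporting. Safety and tolerability of GC4419 given with cisplatin and IMRT is a secondary objective (Section 5.1), and delivery of IMRT and cisplatin is an exploratory one. A reader of the AE tables would expect a laboratory finding that ended a subject's cisplatin to appear there at least as reliably as one that postponed a dose.

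**Working it through.** The plan gives no figure on this point, so the check compares the provisions with one another.

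**Step 1. Coverage of the two treatment-consequence lines (criteria 2 and 4).**

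| Consequence | GC4419/Placebo | IMRT | Cisplatin |
|---|---|---|---|
| Reduction or delay | named | named | named |
| Discontinuation | named | not named | not named |

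**Step 2. Can the two empty cells be filled by interpretation?**
- The Synopsis identifies the investigational product as GC4419, so cisplatin and IMRT do not fall under criterion 4.
- A stop is not safely a form of reduction, because Section 11.2.3 gives discontinuation its own line. Section 12.5.2 names discontinuation of study drug, cisplatin and IMRT together, so the protocol lists all three when it means all three. Section 9.1 describes modification of cisplatin as a lower dose or a changed schedule.

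**Step 3. Other routes into the AE section.** Take an abnormality that stops cisplatin or IMRT while study drug continues. It is still recorded if any of four things is true: it is serious; it is treated; it is Grade 3-4; or it earlier caused a reduction or delay of any of the three treatments. Four yes/no conditions give 2 × 2 × 2 × 2 = 16 combinations, and the event is left out in only one, where all four are absent. This counts combinations and says nothing about how often each occurs.

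**Step 4. The same value, two outcomes.** Consider a Grade 2, non-serious, untreated creatinine rise.
- Subject A has one cisplatin dose postponed. Criterion 2 is met and an AE is entered.
- Subject B receives no further cisplatin from that point, with no earlier delay or reduction, and continues study drug and IMRT. No criterion is met and no AE is entered.

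Subject B's case is possible under the protocol. Section 9.1 leaves cisplatin toxicity to institutional and ASCO guidelines and the Investigator's judgment, and nothing ties a cisplatin stop to Grade 3-4.

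**Step 5. The IMRT cell.** Sections 6.2 and 8.6 give study drug only on days when IMRT is given. Stopping IMRT for good will therefore usually end study drug too and may satisfy criterion 4. In practice the gap is mainly about cisplatin.

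**Step 6. Is the link kept elsewhere?** Section 7.6 requires a CRF reason for ceasing randomized therapy, and no section states the same for cisplatin or IMRT. Section 11.4 records, for each AE, how study drug was managed and what other action was taken, but this presupposes an AE entry. The delivery endpoint in Section 5.2 covers how much was given and when, not why it stopped.

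**The case against.** The best case against the point is that little is left once the other routes are counted. Section 9.1 recommends handling cisplatin toxicity by lowering the dose or changing the schedule, and either step satisfies criterion 2 before any stop. An investigator who diagnoses a renal or hematologic condition can enter that diagnosis as an AE under Sections 11.2.2 and 11.4. The values are not lost: safety laboratory tests are done at least weekly during treatment, each abnormal result is marked for clinical significance (Section 10.1.2), and the incidence and shifts of clinically significant abnormalities are a safety endpoint of their own. Some sites may also read the dropping of all remaining doses as a reduction. All of this stands as a limit on size. It does not supply the missing line, and the last reading sits badly with the separate discontinuation line.

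Three stronger readings are tempting, and the documents support none of them.
- A reader might infer that every abnormality that stops cisplatin or IMRT disappears from the AE tables. Step 3 shows that most routes remain open.
- A reader might infer that the comparison between arms is biased or reversed. The rule is identical in both blinded arms, and nothing in the protocol suggests that the balance of delays and stops differs between them.
- A reader might infer that the exploratory objective "To assess the effects of GC4419 on kidney function throughout the first year post-IMRT" is compromised. It has its own BUN and creatinine measurements at months 3, 6, 9 and 12, independent of AE entry.

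The listing of withdrawals in Section 12.4 is also weak support. A subject who stops cisplatin but stays on study drug and IMRT is not clearly a withdrawal in the sense of Section 7.6.

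**Conclusion.** The concern holds in a narrow form. Section 11.2.3 omits discontinuation of cisplatin and IMRT from an exclusive list. A non-serious, untreated Grade 1-2 laboratory abnormality that leads directly to such a stop, with study drug continuing and no prior delay or reduction, is not recorded as an AE, although a milder consequence of the same value is. What is lost is the link between value and stop, not the value.

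The size cannot be estimated, because the documents give no frequency of low-grade laboratory findings that end cisplatin or IMRT; it may be small. The efficacy analyses are unaffected, since oral mucositis is captured separately as an endpoint (Section 11.2.4). The conclusion assumes that sites apply the list literally and that no CRF page outside these documents ties a cisplatin or IMRT stop to its laboratory cause.

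**What to change.** Reword criterion 2 in Section 11.2.3 to name four consequences (dose reduction, delay, omission and permanent discontinuation) for each of GC4419/Placebo, IMRT and cisplatin. Delete the separate investigational-product line, which then becomes redundant. Including omission also settles how to classify a single skipped dose. Align the CRF completion instructions.

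This changes data capture only and sets no rule on when any treatment should be modified or stopped. The cost is one sentence, an update to site instructions and a few more AE entries. Events already collected follow the old rule, so the safety report should state the date of the change.

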# 11.2.4. Disease-Related Events and/or Disease-Related Outcomes Not Qualifying as AEs or SAEs

Oral mucositis will not be reported as an AE as it is captured as a study endpoint in the CRF. Progressive disease found by scan or on clinical evaluation should be captured on the applicable CRF pages and not as an AE.

# 11.2.5. Grading of Adverse Events

The severity of adverse events will be designated as mild, moderate, severe, life threatening, or fatal per NCI CTCAE version 5.0. If not specifically addressed in NCI CTCAE version 5.0, use Table 5 below:

**Table 5: Adverse Event Severity** 

Grade	Criteria 
Mild – Grade 1	Asymptomatic or mild symptoms; clinical or diagnostic observations only; intervention not indicated
Moderate – Grade 2	Minimal, local, or noninvasive intervention indicated; limiting age-appropriate instrumental ADL 
Severe – Grade 3	Severe or medically significant but not immediately life- threatening; hospitalization or prolongation of hospitalization indicated; disabling; limiting self-care ADL 
Life Threatening – Grade 4	Life-threatening consequences; urgent intervention indicated
Death – Grade 5	Death related to adverse event

A semi-colon indicates 'or' within the description of the grade.

# 11.3. Relationship to Study Drug

All AEs will be categorized by the Investigator with respect to their relationship to GC4419/Placebo. The Investigator should consult the IB and/or product information in the determination of his/her assessment. The relationship between GC4419/Placebo and the AE may

Instrumental ADL refer to preparing meals, shopping for groceries or clothes, using the telephone, managing money, etc.

Self-care ADL refer to bathing, dressing and undressing, feeding self, using the toilet, taking medications, and not bedridden.

be considered related, possibly related, or unrelated. The criteria for each category are listed below:

**Related:** It is likely that GC4419/Placebo caused or contributed to the cause of the adverse event or laboratory abnormality, when the temporal sequence from the time of GC4419/Placebo administration, the known consequences of the subject's clinical/state condition or study procedures, the effects of discontinuing or reintroducing GC4419/Placebo on the adverse event, and other medically relevant factors are considered.

Galera Therapeutics, Inc.

Version: Amendment 4

**Possibly Related:** There is a reasonable possibility that the adverse event or laboratory abnormality was caused by GC4419/Placebo, when the temporal sequence from the time of GC4419/Placebo administration, the known consequences of the subject's clinical state/condition or study procedures, and other medically relevant factors are considered.

**Unrelated:** The Investigator has a high level of certainty that the subject's clinical state/condition, study procedures, or other medically relevant factors other than treatment with GC4419/Placebo caused the adverse event or laboratory abnormality. This relationship category should only be used when a clear precipitating cause exists and it is not reasonably possible that the event is caused by treatment with GC4419/Placebo.

If the relationship between the AE/SAE and the investigational product is determined to be "possibly related" the event will be considered to be related to the investigational product for the purposes of expedited regulatory reporting.

# 11.4. Recording Adverse Events

All AEs must be recorded on the appropriate CRF regardless of the severity or relationship to GC4419/Placebo. All AEs that meet the seriousness criteria should also be recorded on the SAE Report Form. All SAEs must be reported to the Sponsor or delegated organization within the timeline stated in Section 11.2.

The recording of AEs will be based on data obtained from the following sources:

Medical and surgical history

Physical examinations including vital signs

Clinical laboratory test results

Subject verbal reports to the investigational staff and documented in the medical chart

All clinical events, including both observed (such as any reaction at sites of application) and volunteered problems, complaints, or symptoms, are to be recorded. The need to capture this information is not dependent upon whether the clinical event is associated with GC4419/Placebo use. AEs resulting from concurrent illnesses, reactions to concurrent medications or symptomatic progression of disease states are also to be recorded.

The information to be recorded for AEs will include:

The specific type of event in standard medical terminology – diagnosis if known, is preferred over symptoms

Duration of the clinical event (start and stop dates)

Severity (Grade 1, 2, 3, 4, or 5) of the clinical event

Seriousness (SAE) criteria, if applicable

Relationship of the AE to GC4419/Placebo as defined in Section 11.3

Management of GC4419/Placebo administration and other action taken to alleviate the clinical events

Galera Therapeutics, Inc.

Version: Amendment 4

Clinical outcome of the AE

# 11.5. Follow-up of AEs and SAEs

If an adverse event changes in grade within the date of randomization through the 30 Day Reporting Period, the event should be recorded as a new AE.

After the initial AE/SAE report, the Investigator is required to proactively follow each subject and provide further information on the subject's condition. The Investigator will ensure that follow-up includes any supplemental investigations as may be indicated to elucidate the nature and/or causality of the AE or SAE. This may include additional laboratory tests or investigations, histopathological examinations, or consultation with other health care professionals.

Non-serious AEs that have not resolved within 30 days after last dose of GC4419/Placebo will be considered ongoing, and marked as such in the CRF. All SAEs will be followed until they resolve or a new baseline is established, at which point the appropriate CRF page(s) or SAE Report Form(s) will be updated.

Routine collection of AEs will stop 30 days after last dose of GC4419/Placebo, IMRT, or cisplatin (i.e., whichever occurs last); however, collection of clinical data will continue on AEs of interest or as clinical circumstances warrant that exceed the 30 days after last dose of GC4419/Placebo, per below and described in other sections of the Protocol:

- OM: 2 weeks post last IMRT dose (Section 10.10.1)
- Medical events, which in the opinion of the Investigator, serious and are believed to be a result of study participation to warrant notifying the Sponsor (Sections 11.6 and 11.8). In these circumstances, the Investigator should contact the Galera Medical Monitor (or designee) directly to discuss the case, and how it should be reported.

As reasonably requested by the Sponsor, the Investigator will perform or arrange for the conduct of supplemental measurements and/or evaluations to elucidate as fully as possible the nature and/or causality of the AE or SAE. If a subject dies during participation in the study or during a recognized follow-up period, the Sponsor will be provided with a copy of any post-mortem findings, including histopathology.

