#### 4.3. Study Period Definitions

**Study Treatment Period:** the period of time from Study Day 1 (IMRT Day 1/Baseline) through the last day of IMRT. Subjects who receive at least 60 Gy of IMRT will be considered to have completed the Study Treatment Period.

**OM** (**Oral Mucositis**) **Observation Period:** the period of time from Study Day 1 (IMRT Day 1/Baseline) through the last OM assessment. By protocol, the last OM assessment is to occur during the second week after completion of IMRT.

**AE** (Adverse Event) Observation Period: the period of time from the date of randomization through 30 days post last day of cisplatin, IMRT, or GC4419/Placebo (i.e., whichever occurs last).

**LTFU** (**Long-term Follow-up**) **Observation Period:** the period of time from last day of IMRT through 24 months post-IMRT.

Galera Therapeutics, Inc.

Version: Amendment 4

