#### Safety:

Safety of GC4419 as measured by:

- Frequency, duration, and severity of Adverse Events (AEs) and serious AEs
   (SAEs) during the AE Observation Period;
- Incidence and shifts of clinically significant laboratory abnormalities

Effect of treatment on tumor outcomes (locoregional failure, distant metastases, progression-free survival, overall survival) during the LTFU Observation Period

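### Section 11.5 marks non-serious AEs as ongoing on a study-drug-only clock that can run out weeks before the AE Observation Period ends, so resolution dates needed for the AE duration endpoint may go uncollected

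*Combined protocol and SAP*

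**What the plan says.** The safety endpoints in Section 5.2 begin with "Frequency, duration, and severity of Adverse Events (AEs) and serious AEs", assessed over the AE Observation Period. Section 4.3 defines that period as "the period of time from the date of randomization through 30 days post last day of cisplatin, IMRT, or GC4419/Placebo", with the latest of the three governing. Section 11.2.2 gives the same follow-up rule for individual events, which are to be "followed for 30 days after the last dose of IMRT, cisplatin, or GC4419/Placebo (i.e., whichever occurs last". The AE footnote to the Schedule of Assessments (Appendix 1) uses the same window.

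Section 11.5 is not consistent with this. For non-serious events it says: "Non-serious AEs that have not resolved within 30 days after last dose of GC4419/Placebo will be considered ongoing", to be flagged that way in the CRF. The next paragraph returns to the wider window: "Routine collection of AEs will stop 30 days after last dose of GC4419/Placebo, IMRT, or cisplatin (i.e., whichever occurs last". The same sentence then describes its exceptions by counting from GC4419/Placebo alone.

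Sections 7.6, 9.1 and 12.5.2 ask that subjects who stop the infusion go on with cisplatin, IMRT and study assessments.

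**The concern.** A site that reads Section 11.5 literally has a reason to stop looking for the resolution date of a non-serious AE 30 days after the last infusion, even if the subject is still receiving chemoradiation. A site that reads Section 11.2.2 would go on to the later date. The protocol gives two answers to one data-collection question.

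What is at stake is AE duration. A resolution that occurs after the earlier date but inside the AE Observation Period may never be recorded. The problem is concentrated in subjects who leave study drug early, some of them because of toxicity. Section 12.1 lets the SAP govern the analysis where it differs from the protocol, but no analysis rule can supply a stop date that was never collected.

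**Working it through.** The plan gives no figure to reproduce, so the check is calendar arithmetic on the protocol's own schedule.

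**Inputs**
- Monday start and five treatment days a week (Table 3, Section 8.6). The k-th dose or fraction falls on D(k) = 7 × floor((k − 1)/5) + ((k − 1) mod 5) + 1. Check: D(35) = 42 + 4 + 1 = 47, the last day shown in Table 3.
- At most 35 doses of GC4419/Placebo (Sections 6.2 and 8.6).
- 60-72 Gy in fractions of 2.0-2.2 Gy (Section 7.1). At 2.0 Gy, 70 Gy takes 35 fractions and 72 Gy takes 36. D(36) = 49 + 0 + 1 = 50.
- IMRT is taken as the last treatment. Cisplatin given after the last IMRT day would widen every gap below.

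**Formulas**
- Section 11.5 date = last study-drug day + 30.
- End of the AE Observation Period = last IMRT day + 30.
- Gap = last IMRT day − last study-drug day.

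| Last dose | Study-drug stop day | Fractions | 11.5 date | AE period ends | Gap (days) |
|---|---|---|---|---|---|
| 1 | 1 | 35 | 31 | 77 | 46 |
| 5 | 5 | 35 | 35 | 77 | 42 |
| 10 | 12 | 35 | 42 | 77 | 35 |
| 20 | 26 | 35 | 56 | 77 | 21 |
| 30 | 40 | 35 | 70 | 77 | 7 |
| 35 | 47 | 35 | 77 | 77 | 0 |
| 35 | 47 | 36 | 77 | 80 | 3 |

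On a 36-fraction course the largest gap is 50 − 1 = 49 days.

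The 11.5 date falls before IMRT itself ends when stop day + 30 < 47, that is, when study drug stops on Day 16 or earlier. In the Day 12 row the event is marked ongoing on Day 42, five days before the last fraction on Day 47.

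**What the gap touches**
- Resolution dates of non-serious AEs: exposed.
- SAEs: not exposed. Section 11.5 follows them to resolution or a new baseline.
- New AEs: not exposed. Routine collection runs to the later date.
- Planned AE tables: not exposed. Section 12.4 says "Incidence by subject will be tabulated for all treatment-emergent, serious, severe, and treatment-related adverse events", and a subject counts once whether or not a stop date is known.

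**The case against.** The strongest reply is that this is one sentence with two treatments left out, surrounded by text that states the window correctly. Section 10.9 has AEs recorded on all IMRT days, Section 10.10.1 continues AE recording for 30 days after the last of the three treatments, and Section 11.5 itself requires the investigator to follow each subject proactively. Many sites would probably keep updating the record. This stands as a reason to call the loss possible rather than shown. It does not remove the contradiction, because the sentence at issue is the one that specifically tells sites what to do with an unresolved non-serious event.

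Several stronger readings are tempting, and the documents do not support them.

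- **That Section 11.5 closes these AEs.** It marks them as ongoing, which leaves the end date open (censored). The gaps above are days in which a resolution date may not be sought. They are not days subtracted from a recorded duration.
- **That AE frequency also comes out wrong.** By-subject incidence is unchanged, and the text reviewed specifies no table of event counts.
- **That recording each grade change separately ("the event should be recorded as a new AE") is an error.** It is a data-capture convention. Section 11.4 collects start and stop dates and grade for each record, so contiguous records can be rejoined. How they enter a duration summary is left to the separate SAP, whose text was not available for this review.
- **That the arms will be affected unequally.** Stopping for infusion toxicity makes this conceivable, but the documents give no rate by arm, and Section 4.2 describes safety at 90 mg in the Phase 2b study as similar to placebo.

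**Conclusion.** The concern holds in limited form. The sentence in Section 11.5 contradicts Sections 4.3 and 11.2.2 and a later sentence of its own section. For subjects who stop study drug early and continue chemoradiation, it can place the cut-off up to about 46 days too early on a 35-fraction course. For subjects dosed to the end of IMRT the difference is 0 to about 3 days. The consequence is possible missing resolution dates for non-serious AEs, which compromises the AE duration endpoint in that subgroup only.

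The sizes assume an uninterrupted Table 3 calendar with no cisplatin after the last fraction; the stop days are illustrations. The documents do not say how many subjects will stop the infusion early. The 10% early discontinuation in Section 12.2 concerns completion of the IMRT course and cannot stand in for that number. A reader might infer that the duration endpoint as a whole is invalid, but the text does not show this. The point is minor and worth correcting because the correction is simple.

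**What to change.** Reconcile the sentence in Section 11.5 with the AE Observation Period: a non-serious AE is marked as ongoing only if still unresolved 30 days after the last dose of GC4419/Placebo, IMRT or cisplatin, whichever comes last. Check the later clause of the same section that again counts from GC4419/Placebo alone, and carry the wording into the CRF completion instructions. The gap in the table then becomes 0 days for every subject.

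The cost is one sentence of protocol text and some AE records kept open longer at sites. No change to the incidence tables or to the recording of grade changes is needed for this point.
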